8.2 Secondary Objectives

The secondary objectives are to evaluate the efficacy and tolerability of two different dosing regimens of BCT197 added to SoC versus placebo added to SoC in treatment of an acute exacerbation of COPD requiring hospitalisation by measuring the following:

1. Comparison of FEV1 on Days 3, 10, and 14
2. Normalisation evaluation of spirometry parameter (FEV1, forced vital capacity [FVC], and FEV1/FVC) response over time (performed daily from Days 1 to 7, 10, and 14, and Weeks 8, 12 and 26) compared with the most recent test performed within the last 12 months outside an exacerbation (pre-study FEV1, FVC, and FEV1/FVC value)
3. Time taken to improvement of 100 mL in FEV1 compared to Baseline versus placebo
4. Assessment of AUC of FEV1 over time among groups
5. Respiratory rate (RR) normalisation over time (performed daily from Days 1 to 7, 10 and 14) among groups
6. RR at Days 3, 7, 10, and 14 among groups
7. Time to improvement based on EXACT-PRO total score
8. Assessment of AUC of EXACT-PRO over time among groups
9. Evaluate the number of COPD-related deaths among groups
10. Evaluate the number of moderate/severe COPD exacerbations (classified according to European Medicines Agency (EMA)/Committee for Medicinal Products for Human Use (CHMP) guidelines, refer to [Section 11.2.3](#)) over time among groups
11. Evaluate time to next moderate/severe COPD exacerbation
12. Change from Baseline at each inter-visit period and over the entire period of the study in the average EXACT-PRO total score and domain scores
13. Evaluate the use of rescue therapy during the study
14. Evaluate time from hospitalisation until subject is medically ready (COPD-related) for discharge
15. To characterise the PK of BCT197 in adults with COPD.

Safety and tolerability of BCT197

1. Evaluation of each treatment emergent adverse event (TEAE)/SAE (from first dose of study drug until study completion)
2. Evaluation of the incidence of pneumonia from first dose of study drug until study completion
3. TEAEs of special interest: rash, acneiform dermatitis, cervical/vaginal inflammation, headache, pruritus and liver enzymes (aspartate aminotransferase [AST], alanine aminotransferase [ALT], bilirubin)
4. Evaluation of vital signs and laboratory parameters
5. Evaluation of QTc intervals over time at Baseline, Day 1 to Day 7 (daily), Days 10 and 14
6. Quantitative sputum culture over Days 1 to 14 whenever sputum is collected for clinical purposes.

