11.2.3 COPD exacerbations

A COPD exacerbation is defined as “*A sustained worsening of the patient’s condition (dyspnoea, cough and/or sputum production/purulence), from the stable state and beyond normal day-to-day variations, that is acute in onset and necessitates a change in regular medication in a patient with underlying COPD that includes prescriptions of systemic corticosteroids and/or antibiotics or need for hospitalisation*”.

The exacerbations will be classified as moderate or severe as per the EMA/CHMP guideline definition:

- Moderate: exacerbations that require treatment with systemic corticosteroids and/or antibiotics.
- Severe: Exacerbations that require hospitalisation or result in death.

Emergency room (ER) attendance includes any unscheduled visit at any healthcare institution requiring urgent advice associated with systemic steroids (addition or increment of dose). If an ER stay is longer than 24 hours it will be considered severe. If the ER visit is shorter than 24 hours and not related to any prescription of systemic steroids or antibiotics it will not be considered moderate or severe exacerbation.

For the Screening Visit, a current active COPD exacerbation is classified as one that requires hospitalisation, systemic corticosteroids (start of systemic corticosteroid, or increase in the dose of the systemic corticosteroid) and/or antibiotics.

For the documented history of COPD, moderate and severe COPD exacerbations are defined above. Documentation of previous COPD exacerbation could be, but is not limited to, ER or hospital discharge summary, source document notes at the time of the exacerbation, reference letter from the attending physician of the COPD exacerbation, or the medical prescription of the previous COPD exacerbation with antibiotics or systemic steroids prescribed.

For Part 2 (Stabilisation phase) of the study, COPD exacerbation will be considered all moderate and severe COPD exacerbations per the definition above. Exacerbations that do not fulfil these criteria should be reported as an AE (e.g. worsening of symptoms). A COPD exacerbation during Part 2 of the study is not a reason to withdraw the subject from the study, unless deemed necessary by the investigator.

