12.1.2 Recording of Adverse Events

Any relevant observations made at the Screening Visit (prior to signing the ICF) are to be recorded as a pre-existing condition. For the purposes of this study, any detrimental change in the subject's condition, after signing the informed consent form and up to completion of the 26 week follow-up period after the last administration of study drug, should be considered an AE/SAE.

The following variables will be recorded for each AE: verbatim/AE description and date for AE start and stop, severity, seriousness, causality rating, whether or not the AE caused the subject to discontinue, and the outcome. If the severity of the AE changes, a new AE must be recorded.

SAEs and AEs will be recorded starting after signing of informed consent. All SAEs and AEs have to be recorded, whether or not considered causally related to the investigational product or to the study procedure(s).

All ongoing AEs/SAEs should be followed up until resolution or stabilisation or the last visit if in the investigator's opinion, the AE is unlikely to resolve due to the subject's underlying disease.

At any time after the follow-up visit, if an investigator learns of an SAE that can be reasonably related to study drug, he/she should promptly notify the sponsor.

The investigator will assess the intensity of AEs based on the following definitions:

1. Mild (awareness of sign or symptom, but easily tolerated)
2. Moderate (discomfort sufficient to cause interference with normal activities)
3. Severe (incapacitating, with inability to perform normal activities).

It is important to distinguish between serious and severe AEs. Severity is a measure of intensity whereas seriousness is defined by the criteria in [Section 12.1.8](#).

An AE of severe intensity need not necessarily be considered serious. For example, nausea that persists for several hours may be considered severe nausea, but not an SAE. On the other hand, a stroke that results in only a limited degree of disability may be considered a mild stroke but would be an SAE.

For an AE to be a suspected drug-related event, there should be at least a reasonable possibility of a causal relationship between the study drug and the AE.

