7.1.4 Definitions relative to efficacy criteria

7.1.4.1 COPD exacerbation (moderate and severe)

A COPD exacerbation is defined as “*A sustained worsening of the patient’s condition (dyspnoea, cough and/or sputum production/purulence), from the stable state and beyond normal day-to-day variations, that is acute in onset and necessitates a change in regular medication in a patient with underlying COPD that includes prescriptions of systemic corticosteroids and/or antibiotics or need for hospitalisation*”.

The exacerbations will be classified as moderate or severe as per the EMA/CHMP guideline definition:

- Moderate: exacerbations that require treatment with systemic corticosteroids and/or antibiotics
- Severe: exacerbations that require hospitalisation or result in death.

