8.6 Efficacy analyses

This section addresses separately the analyses to be conducted on the primary, secondary and exploratory efficacy variables.

All definitions relative to efficacy and exploratory endpoints are detailed in Section 7.1.4.

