The following figures will be produced for the EXACT-PRO rolling average score:

- Mean EXACT-PRO rolling average score over time by treatment regimen (Acute Exacerbation Phase and Stabilisation Phase separately).
- Mean EXACT-PRO rolling average score change from baseline over time by treatment regimen (Acute Exacerbation Phase and Stabilisation Phase separately).

The same analysis as above will be performed for each of the 3 EXACT-PRO subscores.

8.6.3.11 Number of COPD-related exacerbations during the study derived from 'Acute Exacerbation COPD' form of the eCRF

COPD-related exacerbations during the study derived from the 'Acute Exacerbation COPD' form of the eCRF will be considered for this analysis.

Only COPD exacerbations with symptoms start date \geq first study treatment intake on the form will be included in the analysis. The ‘date when symptoms started’ recorded on the form will be defined as the start date of the COPD exacerbation.

The number and the percentage of patients with COPD exacerbations, the number of COPD exacerbations and the total follow-up time in years will be summarised by treatment regimen.

The rate of COPD exacerbations per patient per year will be calculated for each treatment regimen using a weighted approach (which consists of pooling all patients of a treatment regimen and dividing the total number of COPD exacerbations by the total follow-up time).

The number and the percentage of patients with COPD exacerbations, the number of COPD exacerbations and the COPD exacerbation rate per patient per year as above will also be presented by treatment regimen for each of the following types of COPD exacerbation:

- Mild COPD exacerbations (intensity recorded as ‘Mild’ on the form)
- Moderate COPD exacerbations (intensity recorded as ‘Moderate’ on the form)
- Severe COPD exacerbations (intensity recorded as ‘Severe’ on the form)
- Moderate/Severe COPD exacerbations (intensity recorded as ‘Moderate’ or ‘Severe’ on the form)
- COPD exacerbations resulting in death (i.e. COPD-related deaths; serious criteria ‘Results in death’ ticked on the form)
- COPD exacerbations requiring hospitalisation (i.e. serious criteria ‘Requires in-patient hospitalisation or prolongs existing hospitalisation’ ticked on the form).

Additionally (and more generally), the number (%) of patients with COPD exacerbations and the number of COPD exacerbations will be presented by treatment regimen for each of the following category:

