8.6.3.13 Time to next COPD exacerbation

8.6.3.13.1 Time to next COPD exacerbation derived from ‘Acute Exacerbation COPD’ form of the eCRF

See section 8.6.3.11 for the derivation of COPD-related exacerbations.

Time to next COPD exacerbation will be analysed using the Kaplan-Meier method. Patients without a COPD exacerbation or who are discontinued before having it will be considered as “censored” patients.

For the following study periods: [0-4) weeks, [4-8) weeks, [8-12) weeks, [12-16) weeks, [16-20) weeks and [20-26) weeks, the number of COPD exacerbation-free patients at the beginning of the period, the cumulative number of patients with COPD exacerbation at the end of the period and the probability of having experienced a COPD exacerbation at the end of the period with the associate two-sided 95% CIs will be presented by treatment regimen. The point estimates and the relative two-sided 95% CIs will be presented by treatment regimen for the 75th, 50th and 25th percentiles. A Kaplan-Meier plot will also be presented. Comparisons between treatment regimens will be

performed by means of the log-rank test. The p-values of the pairwise log-rank test comparisons will be displayed on the figure.

A similar analysis using the Kaplan-Meier method will be performed for:

- Time to next mild COPD exacerbation (intensity recorded as ‘Mild’ on the form)
- Time to next moderate COPD exacerbation (intensity recorded as ‘Moderate’ on the form)
- Time to next severe COPD exacerbation (intensity recorded as ‘Severe’ on the form)
- Time to next moderate/severe COPD exacerbation (intensity recorded as ‘Moderate’ or ‘Severe’ on the form).

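### SAP 8.6.3.11 and 8.6.3.13.1 class exacerbations as moderate or severe from a recorded intensity field that neither document ties to the treatment-and-outcome definition in protocol 11.2.3 and SAP 7.1.4.1

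*SAP*

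**What the plan says.** **The definition.** Protocol 8.2, item 10, sets the objective: "Evaluate the number of moderate/severe COPD exacerbations (classified according to European Medicines Agency (EMA)/Committee for Medicinal Products for Human Use (CHMP) guidelines". Protocol 11.2.3 and SAP 7.1.4.1 give the rule. The SAP has "Moderate: exacerbations that require treatment with systemic corticosteroids and/or antibiotics"; severe means hospitalisation or death. Protocol 11.2.3 adds, for emergency-room attendance, "If an ER stay is longer than 24 hours it will be considered severe", which SAP 7.1.4.1 does not repeat. For Part 2, protocol 11.2.3 counts only moderate and severe events as exacerbations: "Exacerbations that do not fulfil these criteria should be reported as an AE (e.g. worsening of symptoms").

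**The analysis.** SAP 8.6 states: "All definitions relative to efficacy and exploratory endpoints are detailed in Section 7.1.4". But SAP 8.6.3.11 tabulates "Moderate/Severe COPD exacerbations (intensity recorded as" Moderate or Severe on the form. SAP 8.6.3.13.1 analyses "Time to next moderate/severe COPD exacerbation (intensity recorded as" Moderate or Severe, and for derivation it points back only to 8.6.3.11. SAP 7.1.4.10 uses the same field with Mild as a third level. Mild, moderate and severe events are also each counted, compared and given their own Kaplan-Meier analysis.

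**Intensity.** Protocol 12.1.2 and SAP 7.1.5.5 define it, for adverse events only, by tolerability and interference with normal activities. Protocol 12.1.2 adds: "An AE of severe intensity need not necessarily be considered serious".

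**Changes from protocol.** The three changes in SAP section 9 do not include a change in how exacerbations are classed.

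**The concern.** The SAP holds two rules for the same label. One asks what treatment the event needed and how it ended; the other asks what someone entered as its intensity. They agree only if the intensity field was completed by the first rule, and nothing in the protocol or SAP says that it was.

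At stake is the meaning of two named secondary endpoints: 10 (number of moderate/severe exacerbations) and 11 (time to the next one). A reader of the results could not tell whether the label means the protocol's class or an investigator's symptom grade. The separate moderate and severe results are more exposed, because there a shift between the two classes also matters.

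**Working it through.** The plan gives no exacerbation rate and no cross-tabulation of intensity against treatment. Its only sample-size figure, 85 per regimen, rests on FEV1 and does not bear on this point. So there is no figure to reproduce; the check is of the text.

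**1. The two rules side by side**

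| Class | Protocol 11.2.3 / SAP 7.1.4.1 | SAP 8.6.3.11 and 8.6.3.13.1 |
|---|---|---|
| Severe | Hospitalisation or death (protocol: also an emergency-room stay over 24 h) | Intensity recorded as Severe |
| Moderate | Systemic corticosteroids and/or antibiotics | Intensity recorded as Moderate |
| Mild | Not defined | Intensity recorded as Mild |

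**2. Is there a link between the columns?** The nearest is the sentence in SAP 8.6 that sends the reader to 7.1.4. It is generic. Within 7.1.4, the rule (7.1.4.1) and the intensity field (7.1.4.10) both appear without reference to each other. SAP 8.8.1 analyses adjudicated moderate/severe events, but it leaves procedures to a charter that is not among the documents and does not define the form's field.

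**3. What could the field mean?** The only intensity defined in either document is the adverse-event scale. The form also carries seriousness criteria (8.6.3.11), and its events enter the adverse-event tables (8.7.1), where events are summarised by maximum severity. An adverse-event reading is therefore open. So is a reading in which the field stores the EMA/CHMP class.

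**4. What follows if the field is not the EMA/CHMP class?**
- Combined moderate/severe (endpoints 10 and 11): a treated or hospitalised event recorded as Mild is dropped. An event that meets neither criterion but is recorded as Moderate or Severe is added; this cannot arise if sites enter only qualifying events.
- A hospitalised event recorded as Moderate still counts in the combined endpoint. It is misassigned only in the separate moderate and severe analyses, as is a treated, non-hospitalised event recorded as Severe.

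**5. What is already available to apply the definition?** The SAP reads these items from the same form: corticosteroid and antibiotic use (7.1.4.13 Criterion 4; 8.6.3.11), hospitalisation (both places), emergency-room admission over 24 h (7.1.4.13 Criterion 4; 7.1.4.14) and death (8.6.3.11). Criterion 4 already treats an emergency-room stay over 24 h as a hospitalisation. The definition can be programmed without new data.

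**The case against.** The best answer is that the gap is one of wording. The eCRF and its completion guidance fix what the field means, and neither is available. Protocol 11.2.3 says that exacerbations will be classed by the EMA/CHMP rule, SAP 7.1.4.1 repeats it, and the analysis sections may simply name the field where that class is stored. This stands as far as it goes: compatible grading cannot be excluded. It does not supply the missing statement, and the operative rule in the SAP remains able to depart from the definition.

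A reader might infer that the text shows the field to be adverse-event intensity. It does not:
- Separate rows for hospitalised and fatal events are no evidence of conflict. They split the severe class, and 8.6.3.12 relies on the death derivation for endpoint 9.
- A Mild level fits either reading; protocol 11.2.3 itself describes visits that are neither moderate nor severe.
- The SAP does not list the form's fields, so a separate severity entry may exist. Criterion 5 in 7.1.4.13 reads fatal exacerbations from the Adverse Event form.

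The mitigation is also real. Hospitalised and fatal events are tabulated with rates, and corticosteroid-only, antibiotic-only and combined treatment with counts. The all-exacerbation count, rate, test and Kaplan-Meier analyses keep events recorded as Mild, and they match the protocol's combined class if sites enter only qualifying events. SAP 8.8.1 adds adjudicated count, rate, proportion and time-to-event analyses. Investigators are blinded, so knowledge of the arm should not drive misgrading; the main expected effect would be imprecision or dilution. Protocol 13.5.1 calls all analyses exploratory. None of this says what the investigator-reported moderate and severe results mean, and the all-event analyses cannot repair the separate classes.

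**Conclusion.** The point holds as a mismatch between the stated definition and the stated derivation. It affects secondary endpoints 10 and 11, and the separate moderate and severe analyses most. The primary FEV1 analysis and the sample size are unaffected.

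The stronger inference, that events were in fact misclassified or that endpoints 10 and 11 are wrong, is not supported. It would need the eCRF or the data. The size of any effect cannot be computed, since it depends on event rates and on how often recorded intensity departs from the rule, and the documents give neither.

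The conclusion assumes only that the protocol and SAP are read as they stand. Given the exploratory setting and the mitigating analyses, the severity is minor to should-fix. What lifts it above a missing detail is that the SAP states a working rule that can contradict its own endpoint definition, when a safer derivation from the same form is at hand.

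**What to change.** Before unblinding:

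1. In SAP 8.6.3.11 and 8.6.3.13.1, derive the class by protocol 11.2.3 and SAP 7.1.4.1. Severe is hospitalisation, an emergency-room stay over 24 h, or death; otherwise, moderate is systemic corticosteroids and/or antibiotics. Add the emergency-room rule to 7.1.4.1 so that it matches the protocol.
2. Name the exact fields. The SAP uses both a hospitalisation item (7.1.4.13) and a seriousness criterion (8.6.3.11), so say which one counts.
3. Cross-tabulate the derived class against recorded intensity and list the discrepancies.
4. State what the intensity field means, and in 8.7.1 name the field that supplies adverse-event severity for these events.

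If the field was in fact completed under the EMA/CHMP rule, steps 3 and 4 will document that. The cost is SAP wording and derivation code; no new data are needed.

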8.6.3.12 Number of COPD-related deaths during the study

See section 8.6.3.11 for the derivation of COPD-related deaths.

The proportion of patients with a COPD-related death during the study will be compared between treatment regimens using Fisher’s exact test (two-sided test at 5% alpha level).

8.6.3.13 Time to next COPD exacerbation

8.6.3.13.1 Time to next COPD exacerbation derived from ‘Acute Exacerbation COPD’ form of the eCRF

See section 8.6.3.11 for the derivation of COPD-related exacerbations.

Time to next COPD exacerbation will be analysed using the Kaplan-Meier method. Patients without a COPD exacerbation or who are discontinued before having it will be considered as “censored” patients.

For the following study periods: [0-4) weeks, [4-8) weeks, [8-12) weeks, [12-16) weeks, [16-20) weeks and [20-26) weeks, the number of COPD exacerbation-free patients at the beginning of the period, the cumulative number of patients with COPD exacerbation at the end of the period and the probability of having experienced a COPD exacerbation at the end of the period with the associate two-sided 95% CIs will be presented by treatment regimen. The point estimates and the relative two-sided 95% CIs will be presented by treatment regimen for the 75th, 50th and 25th percentiles. A Kaplan-Meier plot will also be presented. Comparisons between treatment regimens will be

performed by means of the log-rank test. The p-values of the pairwise log-rank test comparisons will be displayed on the figure.

A similar analysis using the Kaplan-Meier method will be performed for:

- Time to next mild COPD exacerbation (intensity recorded as ‘Mild’ on the form)
- Time to next moderate COPD exacerbation (intensity recorded as ‘Moderate’ on the form)
- Time to next severe COPD exacerbation (intensity recorded as ‘Severe’ on the form)
- Time to next moderate/severe COPD exacerbation (intensity recorded as ‘Moderate’ or ‘Severe’ on the form).

8.6.3.13.2 Time to next COPD exacerbation based on EXACT-PRO total score

COPD-related exacerbations during the Stabilisation Phase based on EXACT-PRO total score will be considered for this analysis.

Appendix C describes the EXACT raw scores and EXACT scoring instructions to compute the EXACT daily scores and event frequency, duration and severity.

Time to next COPD exacerbation during the Stabilisation Phase will be analysed using the Kaplan-Meier method. Patients without a COPD exacerbation or who are discontinued before having it will be considered as “censored” patients.

For the following study periods in the Stabilisation phase: [2-6) weeks, [6-10) weeks, [10-14) weeks, [14-18) weeks, [18-22) weeks and [22-26) weeks, the number of COPD exacerbation-free patients at the beginning of the period, the cumulative number of patients with COPD exacerbation at the end of the period and the probability of having experienced a COPD exacerbation at the end of the period with the associate two-sided 95% CIs will be presented by treatment regimen. The point estimates and the relative two-sided 95% CIs will be presented by treatment regimen for the 75th, 50th and 25th percentiles. A Kaplan-Meier plot will also be presented. Comparisons between treatment regimens will be performed by means of the log-rank test. The p-values of the pairwise log-rank test comparisons will be displayed on the figure.

8.6.3.14 Time from hospitalisation admission until the subject is medically ready for discharge (current COPD)

Time from hospitalisation admission until the subject is medically ready for discharge (current COPD) will be analysed using the Kaplan-Meier method. Only patients with initial hospitalisation for COPD date on or prior to Study Day 1 (i.e. in hospital on Day 1) are included in this analysis. Patients who are discontinued before being medically ready for discharge will be considered as “censored” patients.

For the following study periods: [0-1) days, [1-2) days, [2-3) days, [3-4) days, [4-5) days, [5-6) days, [6-7) days, [7-8) days, [8-9) days, [9-10) days, [10-11) days, [11-12) days, [12-13) days, [13-14) days and [14 days-End of Study], the number of patients not medically ready for discharge at the beginning of the period, the cumulative number of patients medically ready for discharge at the

end of the period and the probability of being medically ready for discharge at the end of the period with the associate two-sided 95% CIs will be presented by treatment regimen. The point estimates and the relative two-sided 95% CIs will be presented by treatment regimen for the 75th, 50th and 25th percentiles. A Kaplan-Meier plot will also be presented. Comparisons between treatment regimens will be performed by means of the log-rank test. The p-values of the pairwise log-rank test comparisons will be displayed on the figure.

